BALF	bronchoalveolar lavage fluid
C _{max}	maximum plasma drug concentration
CA199	carbohydrate antigen 199
CCA	cholangiocarcinoma
CFR	Code of Federal Regulations
COVID-19	coronavirus disease 2019
CRO	contract research organization
CTCAE	Common Terminology Criteria for Adverse Events
DSMB	Data Safety Monitoring Board
eCRF	electronic case report form

Confidentiality Statement

This document [REDACTED] may not be duplicated, copied, altered or removed from company [REDACTED]
without prior approval [REDACTED]

Controlled Quality Management Document

Sponsor: Pliant Therapeutics Inc.

Protocol Number: PLN-74809-PSC-203

STATISTICAL ANALYSIS PLAN

ELF	Enhanced Liver Fibrosis (score)
EoS	end of study
EoT	end of treatment
ERCP	endoscopic retrograde cholangiopancreatography
ET	early termination
FDA	Food and Drug Administration
FSH	follicle-stimulating hormone
GCP	Good Clinical Practice
GDPR	General Data Protection Regulation
GGT	gamma-glutamyl transferase
HIPAA	Health Information Portability and Accountability Act
HIV	human immunodeficiency virus
IBD	inflammatory bowel disease
IC ₅₀	50% inhibitory concentration
IC ₈₀	80% inhibitory concentration
IC ₉₀	90% inhibitory concentration
ICF	informed consent form
ICH	International Council for Harmonisation
IEC	independent ethics committee
INR	international normalized ratio
IRB	institutional review board
IRT	interactive response technology
kPa	kilopascal
LDH	lactic dehydrogenase
LSM	liver stiffness measurement

Confidentiality Statement

This document [REDACTED] may not be duplicated, copied, altered or removed from company [REDACTED]
without prior approval [REDACTED]

Controlled Quality Management Document			
Sponsor:		Pliant Therapeutics Inc.	
Protocol Number:		PLN-74809-PSC-203	
STATISTICAL ANALYSIS PLAN			

MAD	multiple ascending dose
██████████	██████████
MedDRA	Medical Dictionary for Regulatory Activities
MELD	model for end stage liver disease
MR	magnetic resonance
MRCP	magnetic resonance cholangiopancreatography
NCI	National Cancer Institute
NOAEL	no observed adverse effect level
██████████	██████████
OHP	hydroxyproline
PD	pharmacodynamic(s)
██████████	██████████
PIPEDA	Personnel Information Protection and Electronic Documents Act
PK	pharmacokinetic, pharmacokinetics
PROs	participant-reported outcomes
PSC	primary sclerosing cholangitis
pSMAD2/3	phosphorylated SMAD2/3
PTC	percutaneous transhepatic cholangiography
REB	research ethics board
SAD	single ascending dose
SAE	serious adverse event
██████████	██████████
SMAD2/3	family of proteins similar to the gene products of the Drosophila gene 'mothers against decapentaplegic' (Mad) and the C. elegans gene Sma , 2 or 3
TE	transient elastography
TEAE	treatment-emergent adverse event
TGF β	transforming growth factorbeta
TNF α	tumor necrosis factor-alpha

Confidentiality Statement	
This document	██████████ may not be duplicated, copied, altered or removed from company ██████████ without prior approval

Controlled Quality Management Document

Sponsor: Pliant Therapeutics Inc.

Protocol Number: PLN-74809-PSC-203

STATISTICAL ANALYSIS PLAN

UDCA ursodeoxycholic acid

ULN upper limit of normal

Confidentiality Statement

This document [REDACTED] may not be duplicated, copied, altered or removed from company [REDACTED]
without prior approval [REDACTED]

Controlled Quality Management Document	
Sponsor:	Pliant Therapeutics Inc.
Protocol Number:	PLN-74809-PSC-203

STATISTICAL ANALYSIS PLAN

1 INTRODUCTION

This document details the planned statistical analyses for Pliant Therapeutics Inc. Study PLN-74809-PSC-203, “A randomized, double-blind, dose-ranging, placebo-controlled, Phase 2a evaluation of the safety, tolerability, and pharmacokinetics of PLN-74809 in participants with primary sclerosing cholangitis (PSC) and suspected liver fibrosis (INTEGRIS-PSC)”.

The proposed analyses are based on the contents of the [REDACTED]

[REDACTED]

This is a Phase 2a, multicenter, 3-part, randomized, double-blind, dose-ranging, placebo-controlled study to evaluate the safety, tolerability, and PK of once-daily (QD) treatment with PLN-74809 in male and female participants aged 18 to 75 years with an established diagnosis of large duct PSC and suspected liver fibrosis. Part 1 will evaluate 40 mg PLN-74809 and placebo, Part 2 will evaluate 80 and 160 mg PLN-74809 and placebo and Part 3 will evaluate 320 mg PLN-74809 and placebo. Placebo participants will be pooled across the study when comparing to PLN-74809 treatment groups.

Each study part will include an up to 42-day screening period, followed by a treatment period of either 12 weeks (Parts 1 and 2) or at least 24 weeks and up to 48 weeks (Part 3), and finally a 4-week post-treatment follow-up period. Based on regulatory considerations, randomization to dose level in Part 2 of the protocol (80 or 160 mg PLN-74809) was conducted in either parallel or sequential manner.

Each participant in Parts 1 and 2 will participate in the study for approximately 154 days (22 weeks), including screening, treatment, and post-treatment safety follow-up. The duration for Part 3 of the study will be variable depending on the study enrollment rate. The duration of participation will be approximately 238 days (34 weeks) for the last participant enrolled and approximately 406 days (58 weeks) for the first participant enrolled including screening, treatment, and post-treatment safety follow-up. The end of Part 3 will commence once the last participant reaches 24 weeks of treatment. At that time, all study participants will complete their next scheduled visit (End of Treatment [EOT]) and the 4 weeks of follow up (End of Study [EOS]). The end of study is defined as the last visit of the last participating participant.

Confidentiality Statement

This document [REDACTED] may not be duplicated, copied, altered or removed from company [REDACTED]
without prior approval [REDACTED]

	Controlled Quality Management Document	
	Sponsor:	Pitant Therapeutics Inc.
	Protocol Number:	PLN-74809-PSC-203
STATISTICAL ANALYSIS PLAN		

2 STUDY OBJECTIVES

2.1 Primary Objective

The primary objective of this study is to assess the safety and tolerability of PLN-74809 in participants with PSC and suspected liver fibrosis.

2.2 Secondary Objective

The secondary objective of this study is to assess the PK of PLN-74809 in participants with PSC and suspected liver fibrosis.

2.3 Exploratory Objectives

The exploratory objectives of this study are as follows:

- To assess changes from baseline in liver fibrosis biomarkers, [REDACTED] PRO-C3 and Enhanced Liver Fibrosis (ELF) score
- To assess changes from baseline in alkaline phosphatase (ALP)
- To assess changes from baseline in magnetic resonance (MR)-based liver imaging
- To assess changes from baseline in patient-reported outcomes (PROs)

3 ENDPOINTS

3.1 Primary Safety Endpoint

The primary safety endpoint is the incidence of treatment-emergent adverse events (TEAEs).

3.2 Secondary Safety Endpoints

The secondary safety endpoints are:

- Clinical laboratories, including hematology, serum chemistry, coagulation, and urinalysis
- [REDACTED]
- Vital signs measurements

3.3 Secondary Pharmacokinetic Endpoints

The secondary PK endpoints are plasma PLN-74809 concentrations [REDACTED] at each sampling time point.

		Confidentiality Statement
This document [REDACTED]		may not be duplicated, copied, altered or removed from company [REDACTED]

Controlled Quality Management Document

Sponsor:

Pliant Therapeutics Inc.

Protocol Number:

PLN-74809-PSC-203

STATISTICAL ANALYSIS PLAN

3.4 Exploratory Endpoints

The following exploratory endpoints will be reported:

- Liver fibrosis markers (PRO-C3, [REDACTED])
- Liver function markers (ALP, [REDACTED])
- Magnetic resonance (MR)-based liver imaging parameters (Whole liver [REDACTED] gadoxetate MRI relative enhancement (RE), Bile duct [REDACTED] gadoxetate MRI time of arrival)
- PROs [REDACTED]
Partial Mayo Score (PMS) parameters

3.5 Additional Endpoints

The following additional endpoints will be reported:

- FibroScan liver stiffness (kPa)

4 SAMPLE SIZE

The sample size was determined empirically. A sample size of approximately 21 participants per treatment group exposed to PLN-74809 is expected to provide a meaningful evaluation of the safety, tolerability, and PK of PLN-74809 in the target population.

5 RANDOMIZATION

For each planned PLN-74809 dose in each Part of the study, n=21 subjects will be randomized to PLN-74809 and n=7 participants will be randomized to placebo for a total of n=28 and in total, N=112 for 4 PLN-74809 doses (40, 80, 160 and 320 mg).

Approximately 112 participants may be enrolled in this study (28 participants in Part 1, 56 participants in Part 2, and 28 participants in Part 3).

Part 1: 28 eligible participants will be randomized in a 3:1 ratio (40 mg PLN-74809:placebo).

Part 2: 28 eligible participants per cohort (56 in total) will be randomized in a 3:1 ratio (PLN-74809:placebo). PLN-74809 doses administered in each cohort will be 80 mg or 160 mg.

Part 3: 28 eligible participants will be randomized in a 3:1 ratio (320 mg PLN-74809:placebo).

Randomization will be stratified by use of ursodeoxycholic acid (UDCA) (yes/no).

Confidentiality Statement

This document [REDACTED]
without prior approval [REDACTED]

may not be duplicated, copied, altered or removed from company [REDACTED].

	Controlled Quality Management Document	
	Sponsor:	Pliant Therapeutics Inc.
	Protocol Number:	PLN-74809-PSC-203
STATISTICAL ANALYSIS PLAN		

Participants will be centrally randomized at the baseline visit using an interactive response technology (IRT) system, according to a computer-generated randomization scheme. Randomization will occur immediately prior to the first dose (Day 1).

6 PLANNED ANALYSES

The Statistical Analysis Plan (SAP) will be approved prior to unblinding of the data for the Part 1/2 interim analysis. Additional statistical analyses or changes to the statistical analysis after this milestone will be documented in an addendum to the SAP.

6.1 Analysis Populations

Participants excluded from the analysis populations and the reason for their exclusion will be listed in Appendix 16.2 of the CSR.

6.1.1 Screened Participants

Screened participants are those who gave informed consent to participate in the study.

6.1.2 Randomized Participants

Randomized participants are those who were assigned a randomization number.

6.1.3 Safety Population

The safety population is defined as all randomized participants who receive at least 1 dose of study drug. Treatment assignment will be summarized by actual treatment.

6.1.4 Pharmacokinetic Concentration Population

The PK concentration population is defined as all participants in the safety population who have any valid PLN-74809 concentration data not including BLQ values. Treatment assignment will be summarized by actual treatment.

6.1.5 Pharmacodynamic Analysis Population

The PD analysis population is defined as all participants in the safety population who have evaluable baseline and at least 1 evaluable postbaseline PD measurement. Treatment assignment will be summarized by actual treatment.

	Confidentiality Statement	
This document	may not be duplicated, copied, altered or removed from company	

	Controlled Quality Management Document	
	Sponsor:	Pitant Therapeutics Inc.
	Protocol Number:	PLN-74809-PSC-203
STATISTICAL ANALYSIS PLAN		

6.1.6 Efficacy Per Protocol Population

The Efficacy Per-Protocol population will consist of participants from the randomized population without protocol deviations that may significantly impact the interpretation of safety and/or efficacy analyses. Treatment assignment will be summarized by randomized treatment.

[REDACTED]

[REDACTED]

[REDACTED]

6.2 Derived Data

This section describes the derivations required for statistical analysis. Unless otherwise stated, variables derived in the source data will not be recalculated.

6.2.1 Race

When more than 1 race category has been selected for a participant, the race categories will be combined into a single category, labelled “Multiple Race,” in the summary tables. The listings will reflect the originally selected categories.

6.2.2 Body Mass Index

Body mass index (BMI) will be calculated as follows:

$$\text{BMI (kg/m}^2\text{)} = \text{Weight at Screening (kg)} / [\text{Height at Screening (m)}^2]$$

	Confidentiality Statement	
This document		may not be duplicated, copied, altered or removed from company

Controlled Quality Management Document

Sponsor: Pliant Therapeutics Inc.

Protocol Number: PLN-74809-PSC-203

STATISTICAL ANALYSIS PLAN**6.2.3 Baseline and Change from Baseline**

Baseline is defined as the last non-missing value before the participant receives the first dose of study drug. Change from baseline is defined as the difference between baseline and any post-baseline records.

6.2.4 Study Day

Study day will be calculated as the number of days in relation to the first dose of study drug.

- date of event – date of first dose of study drug + 1, for events on or after first dose
- date of event – date of first dose of study drug, for events before first dose

6.2.5 Conventions for Missing and Partial Dates

Dates (historical or during study conduct) will only be imputed if a full date is needed for a calculation or to support a definition.

All dates presented in the individual participant listings will be as recorded on the electronic case report form (eCRF).

Missing / Partial Start / Stop Date of Adverse Events, Medical History and Concomitant Medication

Missing and partial start dates will be imputed solely for the purpose of determining whether an AE is treatment-emergent, medical history is ongoing at Screening, or a medication is concomitant to study treatment.

Partial or missing stop date will be imputed as follows:

If the stop date is completely missing and the event has resolved, or the participant has stopped taking the concomitant medication, the stop date will be imputed as the date of the participant's last clinic visit in the study.

- If only the year is known, the stop date will be imputed as "31-Dec" of that year or as the date of the participant's last clinic visit in the study if in the same year.
- If the month and year are known, the stop date will be imputed as the last day of that month unless the stop date corresponds to the same month as the participant's last clinic visit in which case the date of participant's last clinic visit in the study will be used instead.

Confidentiality Statement

This document [REDACTED] may not be duplicated, copied, altered or removed from company [REDACTED]
without prior approval [REDACTED]

	Controlled Quality Management Document	
	Sponsor:	Pliant Therapeutics Inc.
	Protocol Number:	PLN-74809-PSC-203
STATISTICAL ANALYSIS PLAN		

Missing start date will be imputed as follows:

- If the stop date occurs on or after the start of study drug or the event / concomitant medication is ongoing, the start date will be imputed as the date of the first dose of study drug.
- If the stop date occurs before the start of study drug, the start date of the event / concomitant medication will be imputed as the participant's screening date or the stop date of the event / concomitant medication whichever the earlier.

Partial start date (year present, but month and day missing)

- If the stop date occurs on or after the start of study drug or the event / concomitant medication is ongoing, and the year is the same as the year of first dosing the start date will be imputed as the date of the first dose of study drug whichever is latest. If the year is different from the year of first dosing “01-Jan” will be used.
- If the stop date occurs before the start of study drug, the start date of the event / concomitant medication will be imputed as the “01-Jan” of the same year.

Partial start date (month and year present, but day missing)

- If the stop date occurs on or after the start of study drug or the event / concomitant medication is ongoing, the start date will be imputed as the first day of the same month and year unless this partial start date is in same month as the first dose of study drug in which case the date of first dose of study drug will be used.
- If the stop date occurs before the start of study drug, the start date will be imputed as the first day of the month and year of the partial stop date.

If the start time is missing it will be imputed only in the case where the start date of the concomitant medication / event corresponds to the date of the first dose of study drug. The time will be imputed as the same time as the first dose of study drug. In all other cases the time will not be imputed.

Missing Date of Last Dose

If date of last dose is not present, the date of completion/termination will be imputed as the date of last dose for calculation of study drug exposure.

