6.11 Pooled Placebo

Participants in the placebo group will be pooled across study Parts for summaries and comparison to PLN-74809 treatment groups.

--	--

Controlled Quality Management Document

Sponsor:	Pliant Therapeutics Inc.
----------	--------------------------

Protocol Number:	PLN-74809-PSC-203
------------------	-------------------

STATISTICAL ANALYSIS PLAN**Confidentiality Statement**

This document [REDACTED] may not be duplicated, copied, altered or removed from company [REDACTED] without prior approval [REDACTED].

Controlled Quality Management Document

Sponsor:

Pliant Therapeutics Inc.

Protocol Number:

PLN-74809-PSC-203

STATISTICAL ANALYSIS PLAN**6.12 Baseline and Clinical Characteristics**

Baseline summaries will be presented by treatment group (PLN-74809 dose (40, 80, 160 or 320 mg, All PLN-74809) or Placebo) and overall (PLN-74809 dose and Placebo) for the following variables based on the safety population:

Demographic Data

- Age at informed consent (years)
- Sex
- Ethnicity
- Race, where more than 1 race is selected the participant will be presented under the 'Multiple races' category in the summary but each selected race will be displayed in the listing.

Baseline Characteristics

- Weight at Screening (kg)
- Height at Screening (cm)
- BMI at Screening (kg/m²)
- Fertility status (childbearing potential, postmenopausal, surgically sterile)

Clinical Characteristics

- Duration since diagnosis at baseline (defined as the number of months from start date of first date reported for medical history preferred term "Cholangitis sclerosing" to first dose)
- Use of UDCA (Yes/no)
- Duration of UDCA usage at baseline (defined as the number of months from start date of UDCA to first dose)
- Partial Mayo Score for IBD (for participants with IBD ongoing at screening)

■ [REDACTED]

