6.13 Medical History

Separate tabulations of prior and ongoing conditions at screening will be presented by treatment group and overall for the safety population. All reported medical history data will be listed. Nonpharmacological procedures will be provided as a separate listing.

Confidentiality Statement

This document [REDACTED]
without prior approval

[REDACTED] may not be duplicated, copied, altered or removed from company [REDACTED]

Controlled Quality Management Document

Sponsor: Pliant Therapeutics Inc.

Protocol Number: PLN-74809-PSC-203

STATISTICAL ANALYSIS PLAN**6.14 Prior and Concomitant Medications**

Prior medications are defined as any medications taken prior to the first dose of study drug but stopping before the date of the first dose of study drug.

Concomitant medications are defined as medications taken on or after the date of the first dose of study drug or medications that were taken before the first dose of study drug and stopped after the first dose of study drug.

Prior and concomitant medications will be presented by ATC Level 4 classification and preferred name for each treatment group in the safety population.

All reported medications will be listed.

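### The date rules in SAP 6.2.5 are anchored to first dose and last visit, so they can give medical history the wrong ongoing-at-screening status

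*SAP*

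**What the plan says.** The relevant block of SAP 6.2.5 is headed "Missing / Partial Start / Stop Date of Adverse Events, Medical History and Concomitant Medication", so all three record types share its rules. Start dates are imputed to decide whether an adverse event is treatment-emergent, and also whether "medical history is ongoing at Screening, or a medication is concomitant to study treatment".

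Three of the rules matter here:

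- **Stop date completely missing.** "If the stop date is completely missing and the event has resolved", then "the stop date will be imputed as the date of the participant's last clinic visit in the study".
- **Start date missing, record ongoing or stopped on or after first dose.** "the start date will be imputed as the date of the first dose of study drug". A year-only start in the year of first dosing, and a month-and-year start in the month of first dosing, get the same date.
- **Start month and year known, stop before first dose.** "the start date will be imputed as the first day of the month and year of the partial stop date".

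The screening date is used in only one rule: a missing start on a record that stopped before study drug becomes the earlier of the screening date and the stop date.

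Section 1 allows a screening period of up to 42 days. Section 6.13 calls for "Separate tabulations of prior and ongoing conditions at screening". Section 6.12 limits the baseline Partial Mayo Score to participants whose IBD is ongoing at screening. The readable text defines neither *prior* nor *ongoing* for medical history.

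**The concern.** For adverse events and medications the question is whether something happened on or after first dose. Pushing an unknown start to first dose and an unknown stop to the last visit is the cautious choice there. For medical history the question is what was present at screening, a different and earlier date. Anchors that are cautious for the first question can give a wrong answer to the second.

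At stake is the split between prior and ongoing conditions in the 6.13 tables. If the IBD subset in 6.12 is derived from the same dates, the set of participants contributing a baseline Partial Mayo Score is also at stake.

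**Working it through.** The plan gives no figure to reproduce, so the check runs constructed records through the rules as printed.

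**Assumed dates.** Screening is 25-May-2021. First dose is 25-May + 42 days = 06-Jul-2021, the longest gap Section 1 allows. The last clinic visit is 06-Jul + 16 × 7 = 112 days = 26-Oct-2021, that is 12 weeks of treatment plus 4 of follow-up, as in Parts 1 and 2.

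**Two candidate definitions**, since the SAP gives none:

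- D1: ongoing means start on or before screening, and stop on or after screening or still continuing.
- D2: prior means stopped before screening; everything else is ongoing.

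| True history | What is recorded | Imputed date | D1 | D2 |
|---|---|---|---|---|
| Began 2010, resolved 2015 | full start, no stop | stop 26-Oct-2021 | ongoing: wrong | ongoing: wrong |
| Began 2010, resolved 2015 | neither date | start 06-Jul-2021, stop 26-Oct-2021 | neither class: wrong | ongoing: wrong |
| Began 2010, resolved Feb 2021 | full start, stop year 2021 | stop 26-Oct-2021 | ongoing: wrong | ongoing: wrong |
| Began 2010, resolved 10-May-2021 | full start, stop May 2021 | stop 31-May-2021 | ongoing: wrong | ongoing: wrong |
| Began 2010, resolved 2015 | full start, stop year 2015 | stop 31-Dec-2015 | prior: right | prior: right |
| Began 2010, ongoing | no start | start 06-Jul-2021 | not ongoing: wrong | ongoing: right |
| Began Feb 2021, ongoing | start year 2021 | start 06-Jul-2021 | not ongoing: wrong | ongoing: right |
| Began 2010, ongoing | start year 2010 | start 01-Jan-2010 | ongoing: right | ongoing: right |
| Began Mar 2010, stopped 01-Jun-2015 | start month and year, full stop | start 01-Jun-2015 | prior: right | prior: right |
| Began Mar 2010, stopped 20-Jun-2021 | start month and year, full stop | start 01-Jun-2021 | not ongoing: wrong | ongoing: right |
| Began Mar 2010, stopped 28-May-2021 | start month and year, full stop | start 01-May-2021 | ongoing: right | ongoing: right |

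**What the table shows.**

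1. The missing-stop rule fails under both definitions when the condition in fact resolved before screening.
2. The first-dose start rule fails only under D1. For a month-and-year start in the month of first dosing, the result is wrong only when screening falls in that same month; otherwise the condition really did begin after screening.
3. The start-month rule shifts a known start, by 5 years 3 months in the 2015 example, yet usually leaves the status unchanged. The status changes only under D1, and only when the stop lies between screening and first dose in a later calendar month than screening.

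**The rules also disagree with each other.** Take the condition that stopped on 20-Jun-2021. With its start wholly missing, the rule gives the earlier of 25-May and 20-Jun, which is 25-May: ongoing at screening under D1. With its start recorded as March 2010, the rule gives 01-Jun-2021: not ongoing. More information yields the worse answer. Likewise, with no start date, a condition that ended during screening counts as present at screening, while one that continued does not.

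**The case against.** The strongest reply has four parts.

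**Definition.** The SAP never says that ongoing status requires an imputed start on or before screening. Under D2 the start-date problems do not affect the status. This stands as a limit on the second and third rules. It does not help the missing-stop rule, and Section 6.2.5 does list this status among the purposes of imputing start dates.

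**Recorded status.** The rules take resolved or ongoing status as an input, and 6.2.5 imputes only where a full date is needed. If the tables simply use an eCRF flag, little changes in practice. That is possible, but the readable text does not say it.

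**Scope.** The stop rule speaks of events and medications, so one might argue that history lies outside it. The heading of the block names medical history, and no other date rule for history is visible.

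**A partial stop date.** The start-month rule is worded for a partial stop. Suppose screening is 20-Mar, first dose 25-Apr, and the stop is recorded only as April. The stop then becomes 30-Apr, after first dose; the other bullet applies and keeps the recorded start month. This narrows the problem but does not remove it. In the 2021 example a stop recorded only as June becomes 30-Jun, still before 06-Jul, and the start again becomes 01-Jun.

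A reader might also infer that every ongoing record without a start, and every resolved record without a stop, is misclassified. The document does not support that. A condition that began between screening and first dose is correctly placed after screening, and one that resolved after screening with no stop recorded is correctly called ongoing.

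**Conclusion.** The point holds and is minor. Applying these rules as printed to medical history can give the wrong screening status. The missing-stop rule does so under both definitions, for conditions that resolved before screening and have a known earlier start. The first-dose start rule and the start-month rule do so only if status is judged by imputed start, and the start-month rule only in the narrow window described.

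The effect is confined to the descriptive tables of 6.13 and, if its subset is derived from these dates, the baseline Partial Mayo Score in 6.12. It would be tempting to say that participants with long-standing IBD drop out of that subset. The SAP does not say how the subset is built, and where even an earlier start year is recorded the rule gives 01-Jan of that year, which classifies correctly.

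Adverse-event results are not affected. The start-month rule applies only to records that stopped before first dose, so treatment-emergent and concomitant status stay the same. The number of affected history records cannot be determined from the document.

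**What to change.** In 6.2.5:

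- Restrict the first-dose start rule and the last-visit stop rule to adverse events and medications.
- Classify medical history by its recorded ongoing or resolved status on the eCRF where available, and say so in 6.13. State in 6.12 whether the IBD subset uses the same classification.
- Where recorded status does not settle it, do not let the imputed start of an ongoing condition fall after the screening date, and do not let a missing stop on a resolved condition by itself make it ongoing at screening.
- Do not cap every missing stop at the day before screening. That would label as prior any condition that resolved after screening with no stop recorded.
- In the month-and-year start rule for records that stopped before first dose, change *stop* to *start* in the reference to the partial date.

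The cost is a few lines of text and a small derivation change. If the Part 1/2 interim data have already been unblinded, Section 6 requires the change to go into an SAP addendum.
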